- Clinical status assessed using ordinal scale on Study Days 1, 3, 5, 8, 11, 15, 22, and 29;
- Change in clinical status using change in ordinal scale from Study Day 1 to Study Days 3, 5, 8, 11, 15, 22, and 29;
- Days of supplemental oxygen or worse (i.e., ordinal score of 5, 6, 7, 8) up to and including Study Day 29;
- Days of non-invasive ventilation/high-flow oxygen or worse (i.e., ordinal score of 6, 7, 8) up to and including Study Day 29;
- Whether a subject who has a baseline ordinal score of 5 requires new non-invasive oxygen use or worse (i.e., ordinal score of 6, 7, 8) during the study up to and including Study Day 29 (incidence);
- Days a subject who has a baseline ordinal score of 5 has an ordinal score of 6 or greater up to and including Study Day 29;
- Days of invasive mechanical ventilation/ECMO or worse (i.e., an ordinal score of 7 or 8) up to and including Study Day 29;
- Whether subject who has a baseline ordinal score of 5 or 6 requires new invasive ECMO use or worse (i.e., ordinal score of 7 or 8) during study up to and including Study Day 29 (incidence);
- Days a subject who has a baseline ordinal score of 5 or 6 has an ordinal score > 6 up to and including Study Day 29;
- Whether a subject is alive and without respiratory failure (ordinal score < 7) at Study Day 29;
- Time (days) to ventilation or death from Study Day 1 up to and including first 29 days of being on study.
- Days of hospitalization from date of admission up to and including Study Day 29.
- Values of C-reactive protein (CRP), ferritin, D-dimer, lactate dehydrogenase (LDH), and fibrinogen on Study Days 1, 3, 5, 8, and 11 (while hospitalized); and Study Days 15 and 29 (if attends in-person visit or still hospitalized).

Safety

- Whether a subject died from Day 1 up to and including Study Day 15.
- Whether a subject died from Day 1 up to and including Study Day 29.
- Whether a subject died from Day 1 up to and including Study Day 60.
- Time (days) to death from Study Day 1 up to and including Study Day 29.

- Whether a subject experienced at least one SAE up to and including Study Day 60.
- Whether a subject experienced at least one Grade 3 or Grade 4 AE up to and including Study Day 60.
- Episodes of early discontinuation or interruption of study product administration.

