Oxygenation, non-invasive ventilation/high flow oxygen, invasive mechanical ventilation/extracorporeal membrane oxygenation (ECMO) will be assessed using results of the 8-point ordinal scale. Hospitalization duration will be assessed using admittance and discharge dates. Mortality will be assessed using results from the electronic case report form (eCRF) serious adverse events (SAEs) form. That is, the number of days from Study Day 1 to the date of death.

Safety will be assessed by the following:

- Cumulative incidence of SAEs up to and including Study Day 60.
- Cumulative incidence of Grade 3 and 4 clinical and/or laboratory AEs up to and including Study Day 60.
- Discontinuation or temporary suspension of study product administration (for any reason).
- Changes in WBC count with differential, hemoglobin, platelets, creatinine, total bilirubin, ALT, AST, eGFR, and INR over time (analysis of lab values in addition to AEs noted above).

Clinical labs will be drawn on Study Days 1, 3, 5, 8, 11 while the subject is hospitalized and on Study Days 15 and 29 if the subject is able to return to the clinic or is still hospitalized.

Exploratory endpoints for post-baseline usage of key concomitant COVID-19 treatments (e.g., steroids) summarized by investigational therapeutic and control arms. The details of analyses for all virology and PK exploratory endpoints will be included in a separate analysis plan(s).

The schedule of study assessments is provided in each stage-specific appendix of the SAP.

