	Subgroup	Repeat the primary analysis for this endpoint within each of the following subgroups: 
 Actual baseline ordinal score Baseline steroid use Baseline use of emerging COVID-19 treatments Duration of symptoms prior to enrollment (only using the \leq Median; $>$ Median classification)
9. Incidence of new invasive ECMO use through study Day 29 for subjects with baseline clinical status of 5 or 6;	Primary	
 No covariate adjustment
10. Days a subject who has a baseline clinical status of 5 or 6 has a clinical status > 6 up to and including Study Day 29;	Primary	
 No covariate adjustment
	Subgroup	Repeat the primary analysis for this endpoint within each of the following subgroups: 
 Actual baseline ordinal score Baseline steroid use Baseline use of emerging COVID-19 treatment Duration of symptoms prior to enrollment (only using the \leq Median; $>$ Median classification)
11. Proportion of subjects alive and without respiratory failure at Study Day 29;	Primary	
 No covariate adjustment
12. Time (days) to death or ventilation up to and Including Day 29	Primary	Adjust for the following covariates: 
 Baseline dexamethasone use Actual baseline ordinal score Baseline CRP value (Continuous) Age (continuous)

Endpoint	Analysis	Covariates/Subgroups
13. Days of hospitalization from date of admission by Study Day 29.	Primary	
 No covariate adjustment for this analysis
	Subgroup	Repeat the primary analysis for this endpoint within each of the following subgroups: 
 Actual baseline ordinal score Baseline steroid use Baseline use of emerging COVID-19 treatment Duration of symptoms prior to enrollment (only using the <= Median; > Median classification)
Other Secondary Endpoints: Safety		
1. Values of CRP ferritin, D-dimer, LDH, and fibrinogen on Study Day 1: Study Days 3, 5, 8, 11,15 and 29	Primary	
 No covariate adjustment
2. 14-day Mortality	Primary	1. Adjust for the following covariates: 
 Actual baseline ordinal score Baseline steroid use
3. 28-day Mortality	Primary	1. Adjust for the following covariates: 
 Actual baseline ordinal score Baseline steroid use

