Remaining missing ordinal scores for subjects that terminated early from the study and were still hospitalized at the time of their last assessment or with discharge to a location of hospice, LTAC or other hospital at the time of last contact will be imputed using multiple imputation. A sensitivity analysis of this analysis will be

performed using multiple imputation for all subjects missing ordinal after their last assessment regardless of their discharge status at the last assessment. Details of multiple Imputation are provided in Section 6.5.2.

Some analyses of ordinal score such as those reported in Table 17, Table 18, Table 20, Table 21, Table 24, Table 25, Table 26, Table 27, Table 34, Table 35, Figure 4, Figure 5, Figure 6, Figure 7, and Figure 18 will be based on complete ordinal score data created using the following steps:

- If a subject is discharged from the hospital to a location other than LTAC, Hospice care or other hospital, has intermittent missing ordinal score and reported an ordinal score of 1 or 2 after the missing score then:
 - Impute the intermittent missing ordinal score as 1 if the scores reported before and after the missing value are both 1 and no change in oxygen use or hospitalization status after discharge to a location other than hospice, long term acute care or other hospital.
 - Impute the intermittent missing ordinal score as 2 after discharge to a location other than hospice, long term acute care or other hospital if the subject doesn't fall into the category above and subject is not hospitalized at the time point.
- LOCF will be used for remaining intermittent missingness of ordinal scores for the next planned assessment.
- All missing scores after death will be assigned an ordinal score of 8.
- Subjects discharged from the hospital to a location other than LTAC, hospice care or other hospital at their last assessment will be assigned a score of 2 for all timepoints after last assessment.
- Impute all remaining missing data after last assessment using last observation carried forward.

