13. Days of hospitalization from date of admission by Study Day 29.	Primary	
 If a subject is discharged and no further hospitalization data are available, consider the subject as not readmitted, no additional imputed days will be added. If a subject dies while hospitalized, the number of days of hospitalization will be imputed as the number of days between the date of admission and the expected date of subject's Study Day 29 visit+1.
	Subgroup	
 Use complete data for ordinal score to define this endpoint.

Endpoint	Analysis	Imputation Method
Other Secondary Endpoints: Safety		
1. Values of CRP, ferritin, D-dimer, LDH, and fibrinogen on Study Day 1: Study Days 3, 5, 8, 11,15 and 29	Primary	
 If results are not available for any visit day(s) but are available for visits before or after that visit, the average of the two nearest visits will be imputed for all missing visits between them. If a subject dies or is otherwise terminated early from the study, their last available observation will be carried forward. If baseline is missing, another pre-treatment dose will be used, or the earliest post treatment dose will be used.
2. 14-day Mortality	Primary	
 Subjects whose last assessment in the study is before Day 13 (beginning of Day 29 window) and before death will be considered not dead and censored at the date of their last observed assessment. Subjects who complete follow-up will be censored at Day 15. Deaths that occur after Day 15 will be censored at Day 15.
	Primary with Sensitivity Imputation	
 Subjects whose last assessment in the study is before Day 13 (beginning of Day 15 window) and were discharged to a location other than LTAC, hospice care or other hospital, or subjects died after Day 15 will be considered non-events and censored at Day 15. Subjects whose last assessment in the study is before Day 13 (beginning of Day 15 window) and before death and without being discharged to a location other than LTAC, hospice care or other hospital at their last assessment will be considered non-events and censored at the date of their last observed assessment. Subjects who complete follow-up will be censored at Day 15.

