Ventilator / ECMO days will be defined as the number of days where the ordinal score > 6 up to and including Study Day 29. The total number of days will be the sum of all reported days, regardless of whether the days occur consecutively or in disjoint intervals. For planned gaps between study days, the day of the qualifying Study Day and the days to the next planned Study Day will be included in the total number of days. The Post-Discharge Supplemental Oxygen CRF questions regarding days of ECMO or invasive ventilation will be used for any time period the subject is not hospitalized at the study hospital. See Section 6.5 for the plan for handling subjects who do not have data through Study Day 29 or die prior to Study Day 29.

Duration of Invasive Mechanical Ventilation/ECMO days will be summarized in a table using medians and quartiles by treatment (Table 38). Bee swarm plots of Invasive Mechanical Ventilation/ECMO days, and days hospitalized by treatment will be generated (Figure 21).

The incidence of new Invasive Mechanical Ventilation/ECMO use will be analyzed by treatment (Table 41). The numerator will only include subjects in category 6 or below at enrollment who change to a category 7 or 8. The denominator will include subjects with a baseline ordinal score of 6 or below. The number of subjects reporting new use of Invasive Mechanical Ventilation/ECMO and the incidence rate along with 95% and 80% CIs estimated using the Blaker method will be reported.

Refer to Table 6 for a list of covariates and subgroup analyses for this endpoint. Refer to Table 7 for imputation methods to be applied to this endpoint.

Proportion of Subjects Alive and Without Respiratory Failure at Study Day 29

The proportion of subjects alive and without respiratory failure at Study Day 29 will be defined as the proportion of subjects with an ordinal score < 7 at any time between Day 26 through Day 32 (Visit window for Study Day 29 Visit). The proportion of subjects with respiratory Failure or death at Day 29 will also be provided. These proportions will be presented by treatment along with 95% and 80% Blaker CIs. Treatment differences will be evaluated using a logistic regression and the p-value will be presented (Table 31).

Refer to Table 6 for a list of covariates and subgroup analyses for this endpoint. Refer to Table 7 for imputation methods to be applied to this endpoint.

Time to Mechanical Ventilation or Death up to and Including Day 29

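### Table 7 derives days of hospitalization one way for the overall row and another way for the subgroup rows, and leaves the counting of deaths in the subgroups undefined

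*SAP*

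**What the plan says.** Row 13 of SAP Table 7 (Section 6.5.1) has two entries for days of hospitalization by Study Day 29.

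- **Primary entry.** No days are added after a discharge with no further hospitalization data. For deaths: "If a subject dies while hospitalized, the number of days of hospitalization will be imputed as the number of days between the date of admission". The other end of that interval is given as "the expected date of subject's Study Day 29 visit+1".
- **Subgroup entry.** "Use complete data for ordinal score to define this endpoint".

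Other places bear on this:

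- Section 4.5: "Hospitalization duration will be assessed using admittance and discharge dates".
- Table 6 (Section 6.4.3), row 13, subgroup line: "Repeat the primary analysis for this endpoint within each of the following subgroups".
- Section 6.5.1, on building complete ordinal data: "All missing scores after death will be assigned an ordinal score of 8". Remaining gaps after the last assessment are filled by carrying the last score forward, except that subjects discharged other than to long-term acute care, hospice or another hospital are set to 2.
- Section 3.2 and Table 7 count from the date of admission. Section 8.2.2 starts the count at randomization.
- Section 8.2.2 summarizes the endpoint by medians and quartiles (Table 39), with no test.

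**The concern.** A subgroup row should be the overall analysis restricted to a subset. Here the endpoint itself changes between the overall row and the subgroup rows of the same table. The subgroup rows of the comparable day counts with their own primary imputation rule (Table 7 rows 4, 5 and 8) keep that rule. The row 13 subgroup wording is the same as in row 7, where the primary entry is also ordinal-based, so a carry-over slip is plausible.

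Two programmers following the plan could produce different tables. One would follow Table 6 and use dates. The other would follow Table 7 and count ordinal days, and would then have to decide without guidance which scores make a hospital day. The choice matters most for deaths, because the primary rule turns an in-hospital death into a stay that runs to Day 29.

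**Working it through.** The documents give no figure for this endpoint, so there is none to reproduce. The check counts days for single subjects and then for an illustrative subgroup arm.

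**Inputs.** The subject is admitted *a* days before Day 1, stays in hospital, and dies there on Day *d*. The complete ordinal data hold a hospitalized score on Days 1 to *d* − 1 and score 8 from Day *d* to Day 29. I read the +1 in the primary rule as making the count inclusive.

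**Formulas.**

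- Primary rule, from admission: 29 + *a*.
- Ordinal, score 8 not counted (scores 3 to 7, those labelled as hospitalized): *d* − 1.
- Ordinal, score 8 counted (score 3 or higher): (*d* − 1) + (29 − *d* + 1) = 29.

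| Admission | Death day | Primary | Ordinal 3–7 | Ordinal ≥ 3 |
|---|---|---|---|---|
| Day 1 | 5 | 29 | 4 | 29 |
| Day 1 | 8 | 29 | 7 | 29 |
| 2 days before Day 1 | 5 | 31 | 4 | 29 |
| 5 days before Day 1 | 5 | 34 | 4 | 29 |

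**If score 8 is not counted**, in-hospital deaths become short stays in the subgroups.

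**If score 8 is counted**, other differences remain:

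1. Days from admission to Day 1 are lost if the primary count starts at admission (31 or 34 against 29 above).
2. A subject discharged alive who dies on Day 20 gains 29 − 20 + 1 = 10 days. The primary rule imputes only for deaths in hospital.
3. A subject who leaves the study on Day 6 while still hospitalized has the last score carried to Day 29, adding 29 − 6 = 23 days. The primary row has no rule for this case and adds none.

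Under either reading, Section 8.2.2 asks for one count including COVID-19-related readmissions and one including readmissions for any cause. The ordinal scale cannot separate these, since category 4 covers both.

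**Illustrative arm.** These inputs are assumptions: 50 subjects, survivors' stay lognormal with median 8 days and log-SD 0.7, capped at 29; deaths uniform over Days 2 to 28; admission on Day 1; 4,000 simulated arms. The lowest mortality, 3.5%, equals the Day 8 control-arm death figure in SAP Table 4; the others extend the range.

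| 29-day mortality | Median: primary vs 3–7 | Q3: primary vs 3–7 |
|---|---|---|
| 3.5% | 8.4 vs 8.2 | 13.6 vs 13.0 |
| 10% | 8.9 vs 8.4 | 16.0 vs 13.6 |
| 20% | 10.2 vs 8.8 | 22.7 vs 14.6 |
| 30% | 12.5 vs 9.3 | 27.9 vs 15.5 |

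With score 8 counted, the two rules agree in this simulation, because every subject is admitted on Day 1 and there are no deaths after discharge and no dropouts.

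**The case against.** The strongest reply is that the SAP's own convention counts death in its ordinal day counts: "Days of supplemental oxygen or worse (i.e., ordinal score of 5, 6, 7, 8) up to and including Study Day 29", and "Ventilator / ECMO days will be defined as the number of days where the ordinal score > 6 up to and including Study Day 29". Read that way, an in-hospital death runs to Day 29 in the subgroups too, and on a clock that starts on Day 1 it matches the primary rule exactly. This stands as far as it goes. A reader might infer that early deaths necessarily look like short stays in every subgroup; the documents do not support that, because it requires score 8 to be excluded and the SAP does not say so. The convention does not settle the matter either way. The oxygen and ventilation counts in Section 3.2 state that they include worse states, the hospitalization endpoint in the same list does not, and the scale labels only scores 3 to 7 as hospitalized.

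It is also fair that a survivor with one continuous stay can have the same value under both rules if counting starts at randomization, and that Figure 22 already shows subjects with days imputed for death as a separate group. Finally, complete ordinal data do cover a subject who leaves the study alive while hospitalized, which the primary row does not. That is a gap in the primary row, not a reason to use a second definition for subgroups.

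**Conclusion.** The inconsistency is certain from the text: one endpoint has two derivations, and the subgroup derivation contradicts Table 6 and Section 4.5. The handling of deaths in the subgroup rows is undefined.

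The size depends on a choice that the SAP does not make. With score 8 excluded, the gap is trivial at 3.5% mortality and large at 30%, where the third quartile moves from 27.9 to 15.5 days on the assumed inputs. With score 8 counted, what remains is limited to days before Day 1, deaths after discharge, and dropouts still in hospital.

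A reader might go further and infer that a drug that prevents deaths would look better overall and worse in the subgroups. The documents do not support this. It again needs score 8 excluded, and it concerns means, whereas the SAP reports medians and quartiles. It also depends on the assumed stay: a reversal of half a day in means (15.6 vs 15.1) appears with a median survivor stay of 14 days, but a check with a median of 8 days gave none.

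The consequence is confined to descriptive subgroup summaries of an other secondary endpoint. It does not affect the primary or key secondary analyses or the interim decision. It is worth correcting because the contradiction is plain and the correction is nearly free.

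**What to change.** 1. In Table 7 row 13, replace the subgroup bullet with the sentence already used in subgroup rows 4, 5 and 8, so that each subgroup repeats the analysis with the primary imputation: dates, and the same rule for in-hospital deaths.
2. Reconcile the start of the clock, admission in Section 3.2 and Table 7 against randomization in Section 8.2.2, and use one start in the overall and subgroup rows. Step 1 alone leaves this conflict in place.
3. While editing the row, state in the primary entry how to count a subject who leaves the study alive while still hospitalized. Section 8.2.2 refers to Section 6.5 for subjects without data through Day 29, but row 13 does not cover this case, and step 1 removes the carry-forward that covers it in the subgroups.

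The cost is a few lines of SAP text. No new data are needed, since Section 4.5 already relies on admission and discharge dates.

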² Screening laboratory tests include: ALT, AST, creatinine (and calculate an estimated glomerular filtration rate (eGFR) the formula used is determined by the sites, but should be consistent throughout the study), and urine or serum pregnancy test for females of child-bearing potential. Laboratory tests performed as part of routine clinical care in the 48 hours prior to enrollment will be accepted for determination of eligibility.

³ Baseline assessments should be performed prior to first infusion. Laboratory tests performed as part of routine clinical care in the 24 hours prior to first dose will be accepted for the baseline safety laboratory tests. Baseline may be the same as the screening laboratory tests if obtained in the 24 hours prior to first dose.

⁴ Safety laboratory tests include WBC with differential, hemoglobin, platelets, creatinine, total bilirubin, ALT, AST, and INR.

⁵ Any laboratory tests performed as part of routine clinical care within the specified visit window can be used for safety laboratory testing. ⁶ In-person visits are preferred but recognizing quarantine and other factors may limit the subject's ability to return to the site for the visit. In this case, the visit may be performed by phone.

- If still hospitalized at Day 15 and 29 or returns for an in-person visit: assess adverse events, collect clinical data, vital signs, safety laboratory tests, and research laboratory samples (OP swab and blood) as able.
- If phone call only on Days 15 and 29 and all Day 22 and Day 60 visits: assess adverse events, clinical status (ordinal scale), readmission to a hospital, and mortality only.

⁷ Oropharyngeal swabs are preferred, but if these are not obtainable, saliva or nasopharyngeal or nasal swabs may be substituted. ⁸ Pre-dose serum sample collections for PK and immunogenicity.

⁹ To include markers of inflammation and coagulation: CRP, ferritin, fibrinogen, d-dimer.

¹⁰ Day 8, 22 and 60 visits performed by phone call or home visit if discharged from the site hospital: assess adverse events, clinical status (ordinal scale), readmission to a hospital, and mortality only.

¹¹ Only collected at selected sites capable of processing.

¹² Steroids and other concomitant therapies intended as specific treatment of COVID-19, as well as all biologics, will be assessed from 7 days prior to enrollment to Day 29. All other concomitant medications will be assessed from 7 days prior to enrollment to Day 15 or upon discharge, whichever comes first.

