The study will include one Master Protocol (DMID Protocol 20-0013: ACTIV-5/Big Effect Trial) and an additional “stage” for each investigational intervention included in the study. Stage-Specific Appendices will be provided, detailing the protocol interventions and any specific exceptions to the Master Protocol. One or more interventions/stages may be started at any time. The number of interventions/stages enrolling concurrently are programmatic decisions and will be based on the number of sites and the pace of enrollment. At the time of enrollment, subjects will be randomized to a stage, and then to either the active arm of that stage or the matching placebo. There will be approximately 100 subjects in each active arm of the platform trial (though this may be modified as specified in each stage-specific appendix to accommodate special circumstances). A given site will generally have no more than 3 interventions/stages at once.

See the schedule of assessments in each stage-specific appendix for assessment details. The schedule is similar to Adaptive COVID-19 Treatment Trial (ACTT) to allow evaluation of endpoints used in the larger study. Subjects will be assessed daily while hospitalized. Once subjects are discharged from the hospital, they will have a study visit on Study Days 8, 15, 22, 29 and 60 as an outpatient. The outpatient Study Days 8, 22 and 60 visits do not have laboratory tests or collection of samples and may be conducted by phone. Days 15 and 29 visits are preferred to be in person in order to collect safety laboratory testing, stored samples, and virologic assessments. However, if infection control considerations and other restrictions limit the ability to have visits at Study Days 15 and 29 in person, they may also be conducted by phone and only clinical data will be obtained.

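### The imputation rule for CRP, ferritin, D-dimer, LDH and fibrinogen ignores elapsed time and creates values after death; after discharge its flat average is too high at the later gap days

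*SAP*

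**What the plan says.** Table 7 in SAP section 6.5.1 has one row for CRP, ferritin, D-dimer, LDH and fibrinogen. Its trigger is "If results are not available for any visit day(s) but are available for visits before or after that visit"; its remedy is that "the average of the two nearest visits will be imputed for all missing visits between them". It continues: "If a subject dies or is otherwise terminated early from the study, their last available observation will be carried forward". A further sentence covers a missing baseline and is not at issue here. The row has no sensitivity imputation.

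The sampling schedule is in SAP section 3.2 and the protocol's Schedule of Assessments. Markers on Days 3, 5, 8 and 11 are taken while the subject is in hospital, and those on Days 15 and 29 only from subjects who attend in person or are still inpatients. SAP section 4.1 adds: "The outpatient Study Days 8, 22 and 60 visits do not have laboratory tests or collection of samples". Days 15 and 29 may also be done by phone, without blood.

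The other safety laboratory values follow the same visit days, yet Table 7 row 10 leaves them unimputed.

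**The concern.** A marker gap usually means that the patient went home. The rule then averages an in-hospital value with a convalescent one and gives that single number to every visit in between. A marker that falls steeply at first has already dropped well below the midpoint by the later gap days, so the imputed values there are too high. The arm with more early discharges receives more of them, and a real difference between arms can be diluted. Carry-forward after death adds numbers for subjects who could not be sampled.

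Section 6.5.1 applies Table 7 to primary and secondary outcomes in the mITT and ITT analyses. The markers are tested visit by visit in Table 82, plotted in Figures 31 to 35 and listed for the global analysis in Table 9.

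**Working it through.** **No stated figure to reproduce.** The SAP gives no power, SD or missing-data rate for the markers. One SAP input is used below, the control-arm distribution in Table 4. Re-simulating Table 5 from it gave power at alpha 0.20 of 0.097, 0.594 and 0.908 for OR 1, 1.5 and 2, against the stated 0.096, 0.604 and 0.913, so the input is sound.

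**How many subjects have no inpatient Day 8 sample.** Control: 34.6% discharged + 3.5% dead = 38.1%. At OR 2, the large effect named in SAP section 4.2:
- discharged odds: 2 × 0.346/0.654 = 1.058, so 1.058/2.058 = 51.4%;
- alive odds: 2 × 0.965/0.035 = 55.1, so dead = 1/56.1 = 1.8%;
- total on active: 53.2%.

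Gaps are therefore common, and unequal between arms if the drug speeds discharge.

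**Size of the error in one subject (assumed kinetics).** CRP(d) = max(3, 60 × 2^(−(d−3)/h)) mg/L; last inpatient sample Day 3; imputed value = (60 + next result)/2.

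| h (days) | Next sample | Imputed | Day 5 ratio | Day 8 ratio | Day 11 ratio | Day 15 ratio |
|---|---|---|---|---|---|---|
| 2 | Day 15 (3.0) | 31.5 | 31.5/30.0 = 1.05 | 31.5/10.6 = 2.97 | 31.5/3.75 = 8.40 | sampled |
| 4 | Day 15 (7.5) | 33.75 | 33.75/42.4 = 0.80 | 33.75/25.2 = 1.34 | 33.75/15 = 2.25 | sampled |
| 2 | Day 29 (3.0) | 31.5 | 1.05 | 2.97 | 8.40 | 31.5/3 = 10.5 |
| 4 | Day 29 (3.0) | 31.5 | 31.5/42.4 = 0.74 | 31.5/25.2 = 1.25 | 31.5/15 = 2.10 | 31.5/7.5 = 4.2 |

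The error is upward at late gap days and can be downward at the first.

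**Flat average against interpolation on the log scale.** Take Day 5 = 80 and Day 15 = 5. The rule gives (80 + 5)/2 = 42.5 on both Day 8 and Day 11. Log-linear interpolation gives 80 × (5/80)^0.3 = 34.8 and 80 × (5/80)^0.6 = 15.2.

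**Between-arm difference, setting A (assumed).** Baseline CRP is lognormal, median 100, SD of log 0.8. Half-life is 2 or 3 days in subjects discharged on Days 4 to 7 and 6 days in the rest; residual SD of log 0.3. Discharged: 34.6% against 51.4%. Of the discharged, 40% miss Day 15, and 0% or 40% miss Day 29. The drug acts only through faster recovery and discharge.

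| Day 11 mean difference, mg/L | Range |
|---|---|
| True | −4.9 to −6.8 |
| Table 7 rule | −0.6 to −2.8 |
| Log-linear interpolation | −4.0 to −5.4 |
| Observed values only | −0.25 to +0.7 |

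Loss under the rule: 1 − 2.8/6.8 = 59% to 1 − 0.6/4.9 = 88%. Other choices for details left open, such as later discharge days, gave losses of 50% to 75%, so this is an order of magnitude.

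**Between-arm difference, setting B (assumed).** 100 per arm; median CRP 80; half-life 2, 3 or 5 days, 25% shorter on drug; 40% or 90% return for outpatient blood; 200 runs per scenario, so power is within about ±0.07.
- Discharge OR 2: the rule keeps 52% to 70% of the Day 11 difference. Half-life 2 days, 90% returning: true 9.8 − 6.9 = 2.9, rule 15.6 − 14.1 = 1.5, and 1.5/2.9 = 52%. Half-life 5 days, 40% returning: true 33.5 − 23.8 = 9.7, rule 39.8 − 33.0 = 6.8, and 6.8/9.7 = 70%. Power is 0.12 to 0.22 under the rule, 0.33 to 0.64 with log-linear interpolation, 0.16 to 0.30 with observed values only and 0.60 to 0.78 with full data.
- Discharge OR 1: the rule keeps 96% to 150% of the difference, so there is no real shrinkage. Power is still 0.38 to 0.59, against 0.63 to 0.80 with full data.

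**The case against.** Four stronger readings are tempting, and the documents do not support them.

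*The rule fills every skipped visit.* It does not. An average needs a result on each side, although the trigger is worded as if one side were enough. A discharged subject seen only by phone on Days 15 and 29 has no later result and has neither died nor terminated; the text does not clearly cover that case.

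*The rule hides the drug's pharmacodynamic effect.* The dilution is conditional on faster discharge on drug and on kinetics that the documents do not give. The mechanism-specific markers, IL-17A, IL-22 and IL-1b, are exploratory and fall outside this row.

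*Dropping imputation cures the problem.* In setting A, observed values lose nearly all of the Day 11 difference, more than the rule does, because early-discharged subjects have no Day 8 or Day 11 sample and inpatients are compared with inpatients. In setting B the observed mean difference survives (for instance 12.0 − 8.8 = 3.2 against a true 2.9), but power is only 0.16 to 0.30. A repeated-measures model on log values is no full rescue either. In setting A the true Day 11 geometric mean ratio is 0.72 to 0.83; the model gives 0.89 to 0.92 and the rule 0.93 to 0.98. On Day 8 the model (0.89 to 0.93) is no better than the rule (0.87 to 0.93).

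*Every marker output is affected.* That Table 82 and Figures 31 to 35 use imputed values is an inference: they are Safety-population displays, and SAP section 9.6 does not mention imputation. Tables 44 and 45 are optional.

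It is also fair to say that no decision rests on these markers. What remains is that the flat average and the post-death carry-forward are plainly written, the gaps follow outcome, and a better rule is available.

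**Conclusion.** The point holds for gaps with a result on each side and for values after death. With an assumed CRP half-life of 2 to 4 days, the imputed value is 1.25 to 3.0 times the true one on Day 8 and 2.1 to 8.4 times on Day 11; on Day 5 it is 0.74 to 1.05 times. If the drug also speeds discharge at OR 2, the Day 11 mean difference is diluted by about 60% to 90% in setting A and 30% to 48% in setting B. The direction is the same in both; the size depends on the assumptions. Without a discharge difference there is no shrinkage.

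The primary endpoint, the promising/futile decision and the IL-17A, IL-22 and IL-1b analyses are untouched. This is worth correcting because it is cheap, not because it threatens the trial's main conclusion.

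**What to change.** In Table 7, Safety row 1:

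1. Replace the flat average with linear interpolation in time on the log scale between the two bracketing samples. Reconcile the trigger with the remedy, so that it applies only when there is a result on both sides. The footnote to Table 82 already sets CRP reported as <3.0 to 2.9 and D-dimer reported as <220 to 219, so these have a logarithm.
2. Create no values after death.
3. State that trailing gaps in subjects followed by phone stay missing.
4. Report the number alive and sampled at each visit, and say whether Table 82 and Figures 31 to 35 use observed or imputed values.
5. Show observed-only Day 8 and Day 11 summaries as a supplement labelled as inpatients only, not as the between-arm comparison.
6. Optionally, add a repeated-measures model on log values as a sensitivity analysis.

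The cost is SAP wording and a little programming, with no new samples. The downside is that interpolation assumes log-linear decay between samples. It kept most but not all of the true difference: in setting A, −4.0 to −5.4 against −4.9 to −6.8.
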